To address Hypothesis 2, a repeated-measures ANOVA (with a random effect for subject) will first be used to compare means of key kinematic measures of LOB responses between environments (real-world vs lab). Second, we will compare statistical variability by examining the model residuals between real-world and lab environments using hypothesis testing (essentially Levene's test) and interval estimation to quantify potential differences in variability.

Hypothesis 3: NT and TT participants will exhibit improved LOB responses after lab-induced trips and slips compared to ST participants.

To address Hypothesis 3, response variables will be compared between NT, TT, and ST participants using a one-way ANOVA with group as the independent variable and covariates included as needed. A significant effect of group will be followed by post-hoc analysis using Dunnett's test to determine whether NT, TT, or both differ from ST.

Hypothesis 4: NT and TT participants will exhibit statistically-equivalent LOB responses after lab-induced trips and slips.

To address Hypothesis 4, agreement of response variables between NT and TT participants will be evaluated using statistical equivalence test.

A comparison between the three balance training exercises on LOB responses after any naturally-occurring real-world trips will be done qualitatively and thus not have an explicit hypotheses to be tested.

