To address our secondary objective, balance training participants will be assigned to one of three balance training exercises/interventions including TT, NT, and ST. No drugs are used in this study. Each training session for TT, NT, and ST will be one-on-one with the investigator, approximately 30-45 minutes in duration, and two sessions will be completed each week for three weeks. A description of each session of each type of training follows.

Each TT session will involve a trip training protocol with a specialized treadmill (Aviles et al., 2019). TT perturbations will be induced while participants are standing on a modified treadmill (Freemotion 800, Freemotion Fitness, Logan, UT). The treadmill belt will then be accelerated posteriorly, varying in speed from 0.5 to 2.4 mph, to induce a forward LOB within about 40 msec. Participants will be instructed to react naturally and try to establish a stable gait after perturbations and an initial step over an obstacle. The treadmill belt speed will be maintained until one of two conditions are met: (1) participant established a stable gait for several strides, or (2) participant received substantial support from a fall protection harness or spotter(s) standing next to him/her. Based upon the performance of participants, the treadmill speed will progressively be increased during each session to continue challenge participants and to maintain variability over the course of training. Perturbations in the reverse belt direction (i.e., 0.5 mph anteriorly) will also be included intermittently to reduce anticipation. A slender, lightweight rectangular foam block (7.5 cm x 7.5 cm cross section) will be placed within 3-7 cm in front of the toes before each trial to elicit a step over an obstacle, similar to that needed during an actual trip. Given the suddenness of these perturbations, participants will wear a fall protection harness supported by an overhead gantry to protect knee or hand from contact with the treadmill in the event of an unsuccessful attempt to recover balance. Each TT session will involve exposure to up to 40 treadmill perturbations with a rest break after every 10 perturbations.

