- Participants will first complete a minimum of 10 walking trials along a 12-meter-long walkway at a self-selected speed. Instructions will be to “walk as if you have somewhere to go, and if tripped or slipped, recover your balance and continue walking.” All participants will wear the same model of rubber-soled shoes and a safety harness affixed to a ceiling-mounted track that spans the length of the walkway. After initial walking trials, trips and slips will be induced during randomly-selected trials with walking trials and rest breaks interspersed. As in our prior work, trips will be induced using a tripping obstacle that is initially concealed and level with the walkway. Upon proper placement of the foot relative to the obstacle while walking, the obstacle will be activated and quickly rise and result in a trip shortly after mid-swing. In an effort to add variety to the LOB responses, three trip obstacle heights from prior tripping studies will be used including 5, 7.5, and 10 cm. Slips will be induced using the same methods and distraction efforts as in our preliminary studies. While the participant is facing away from the walkway and distracted, a contaminant or slipping hazard applied over a 0.9×0.9 m targeted section of the walkway to induce an unexpected slip at heel strike during the next trial. In an effort to add variety to the LOB responses, three different contaminants or slipping hazards will be used including vegetable oil, soapy water, and a carpet mat on a polished vinyl floor.

Measure naturally-occurring LOB responses in the real-world:

- Participants will be briefed on how to wear and use the wearable sensors, and the investigator will give the sensors to the participants for them to wear over the subsequent three weeks (no balance training participants) or two weeks (TT, NT, and ST participants) during their daily lives. Participants will be asked to wear the sensors for at least 10 hours a day.

21-1072 Validation and application of wearable sensors for capturing responses to losses of balance

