8.6 Include a description of any deception to be used in the study. Include justification for the use of deception (why the deception is necessary), describe the debriefing process, and describe how the study meets all the following criteria for alteration of consent (deception is considered an alteration of informed consent):

- The research involves no more than minimal risk to the subjects*
- The alteration will not adversely affect the rights and welfare of the subjects*
- The research could not practicably be carried out without the alteration/deception*
- (Optional but encouraged in most cases) Subjects will be provided with additional pertinent information after participation (i.e., debriefing for studies involving deception)*

Incomplete disclosure will be used in that we will not describe some details of parts of the laboratory session for balance testing. In particular, we will not disclose 1) whether participants will be slipped or tripped; 2) when during their multiple walks along our laboratory walkway they will be slipped or tripped; and 3) exactly how we will cause them to slip or trip.

This is necessary so that our testing involves unexpected slips and trips.

At the end of the laboratory session that involves exposing participants to slipping and tripping, we will provide a debriefing by reading the attached debriefing script.

8.7 *If the study involves long-term follow-up (once all research related procedures are complete), describe what data will be collected during the follow up period and when it will occur:*

The study does not involve long-term follow-up.

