14.3 If applicable, indicate the number of potential subjects you expect to screen for enrollment, and the number of subjects you will need to complete the research procedures:

N/A

14.4 If the study has more than one procedure, indicate the total number of subjects to undergo each procedure separately:

30 participants will be assigned to be non-balance training participants

30 participants will be assigned to be balance training participants, with 10 completing each of the three types of training under investigation (TT, NT, ST).

Other than these differences in balance training, all other testing will be the same for all participants.

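### Does Hypothesis 3 need a stated value per participant and a stated rule for combining trips and slips before its error rate can be trusted?

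*Combined protocol and SAP*

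**What the plan says.** Section 5.2 states Hypothesis 3 as "NT and TT participants will exhibit improved LOB responses after lab-induced trips and slips compared to ST participants". The test is that "response variables will be compared between NT, TT, and ST participants using a one-way ANOVA with group as the independent variable", with covariates as needed. A significant group effect leads to Dunnett's test of the non-treadmill (NT) and treadmill (TT) arms against ST.

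In the lab session of section 8.2, "trips and slips will be induced during randomly-selected trials with walking trials and rest breaks interspersed". For trips, "three trip obstacle heights from prior tripping studies will be used including 5, 7.5, and 10 cm". For slips, "three different contaminants or slipping hazards will be used including vegetable oil, soapy water, and a carpet mat on a polished vinyl floor". The number of perturbations each person receives is not given. Section 14.4 adds: "Other than these differences in balance training, all other testing will be the same for all participants". Section 8.6 withholds the details of the session and explains: "This is necessary so that our testing involves unexpected slips and trips".

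Section 14.1 sizes the training arms on Hypothesis 3 using trip data only: a 17.4° difference in trunk angle, a standard deviation of 12°, and a one-sided 5% t-test with 80% power. That gives seven per group, with ten recruited.

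**The concern.** Two choices are open.

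- **Which value.** If each person meets several trips and several slips, the analysed value could be the first exposure, a mean or the response at one hazard level. These differ in meaning, because only the first exposure in a session is free of carry-over from earlier ones.
- **Which result counts.** The hypothesis names trips and slips together. The plan does not say whether they are pooled. If they are separate, it does not say whether one significant result is enough. Dunnett's test covers the two comparisons with ST and does nothing about trips versus slips.

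If these choices were made after seeing the data, a nominal 5% test would have more than one chance to succeed. The sizing offers little help on slips, and the training leans towards trips (section 7.1: "Each TT session will involve a trip training protocol with a specialized treadmill"), so the two perturbation types could well give different answers. At stake would be both the false-positive rate and the power of the hypothesis that set the size of the training arms.

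**Working it through.** **Inputs.** From section 14.1: difference 17.4°, SD 12°, one-sided alpha 5%, seven needed and ten recruited per group. From section 5.2: one-way ANOVA, then Dunnett against ST. Assumptions: ANOVA alpha 5% (not stated in 5.2), one response variable, one trip value and one slip value per person with correlation 0.2, 0.5 or 0.7, and NT equal to TT when there is a benefit.

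**1. The plan's own figure.** d = 17.4/12 = 1.45. Exact one-sided t-test power is 75.5% at six per group, 81.9% at seven and 92.9% at ten. The stated seven reproduces. It treats each participant as contributing one value.

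**2. Is each candidate analysis valid by itself?** Yes. Simulated under no effect (three trips and three slips per person, six splits of the variance), the ANOVA on the mean trip, the mean slip or the first trip rejects in 4.9% to 5.1% of trials.

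**3. ANOVA step only, trips or slips.** If the two were independent, the chance of at least one rejection is 1 − 0.95² = 9.75%. With correlated values it is 7.5% to 9.6% on means and 8.5% to 9.7% on first exposures. If first or mean may also be picked afterwards, it is 11% to 16%. These are the figures that look alarming.

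**4. The full sequence.** An ANOVA rejection caused by NT differing from TT, or by ST doing better, does not support Hypothesis 3. Requiring a significant ANOVA, then a two-sided Dunnett difference (critical value about 2.33 at ten per group) showing improvement over ST, gives these false-positive rates under no effect:

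| Rule | At least one arm beats ST | Both arms beat ST |
|---|---|---|
| Trips or slips, either suffices | 3.2%–3.7% | 0.4%–0.5% |
| Free choice among first or mean, trip or slip | about 4.2%–6.2% | under 1% |

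For one perturbation type with at least one arm beating ST, the rate is about 1.9%. As a check on the first row, two independent chances at 1.9% give 1 − (1 − 0.019)² = 3.8%, and correlation brings this down slightly. If both trips and slips must be significant, even the ANOVA step alone rejects for both in only about 0.2% to 2% of trials.

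**5. Power.** With NT and TT both 1.45 SD better than ST on trips, the noncentrality is 10 × (2/3) × 1.45² = 14.0 and the ANOVA has 90% power (0.896). If the slip benefit is assumed to be half as large, Hypothesis 3 is supported as follows:

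| Rule | At least one arm beats ST | Both arms beat ST |
|---|---|---|
| Either type suffices | 90%–92% | 71%–74% |
| Both types required | 30%–33% | 10%–13% |

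With equal benefits on trips and slips, the ANOVA step gives 95% to 98% if either type suffices and 81% to 84% if both are required.

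**The case for a change.** The strongest case for a change is that nothing in the protocol closes the gap. Even with one trip and one slip per person there are two results and no rule, and the training arms were sized on this hypothesis. Allowing either type nearly doubles the error rate relative to a single test. The probability of success can move from about one in three to nine in ten on an unwritten rule. A few sentences in 5.2 would settle it at no cost in visits or participants. Hypothesis 4 uses the same responses and shares the gap.

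The omission and the spread in power stand. Three points weaken the case for a required change.

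- The claim that error exceeds 5% holds for the ANOVA step, not for the directional claim that the plan tests. Only a free after-the-fact choice among four values reaches or slightly passes 5%. Against a stricter one-sided 2.5% standard the either-type rule would exceed the limit, but section 14.1 works at one-sided 5%.
- Several perturbations of each type per person is an inference. Section 8.2 introduces the heights and hazards as a way to vary the responses and does not say that everyone meets each level. The uniform-testing sentence in 14.4 cannot settle this, since sections 5.1 and 8.2 give different sensor periods and a different order of lab session by group.
- Each candidate remedy carries its own cost. Testing trips first means a slip-only benefit could not be confirmed. Holm's method lowers single-trip power to 83% at worst. Requiring both types lowers power further. None of them corrects a stated rule that gives a wrong answer.

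**Conclusion.** This is missing detail that an analyst can fill sensibly. The posttest-only design, the between-group wording and the t-test sizing all point to one value per participant, and any of the natural values gives a valid 5% ANOVA. Read literally, the hypothesis joins trips and slips, which is the cautious reading. Under the lenient reading the full sequence still gives a false-positive rate of 3.2% to 3.7%, and 0.4% to 0.5% if both training arms must beat ST. Presenting trip and slip results separately lets a reader apply either rule.

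What remains is that the chance of success depends on the rule: 90% to 92% against 30% to 33% in the half-benefit case. That is worth keeping in mind when the results are interpreted, but it reflects how ambitious a claim the investigators wish to make on a secondary objective with ten per arm.

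The conclusion rests on a 5% ANOVA level, one response variable, trip–slip correlations of 0.2 to 0.7 and a two-sided Dunnett test. It would weaken if the value and the perturbation type were both chosen freely after the data were seen. No change to the plan follows.

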6.0 Setting

6.1 *Describe the sites or locations where your research team will conduct the research. Consider each of the items listed below:*

- *Identify where your research team will identify and recruit potential subjects.*
- *Identify where the team will perform the research procedures.*
- *Describe the composition and involvement of any community advisory board(s).*
- *For research conducted in other locations, describe:*
 - *Site-specific regulations or customs affecting the research at those locations.*
 - *Local scientific and ethical review structure at those locations. Examples include work in other cultures or ethnic groups (within or outside of the U.S.) and work with churches. The HRPP will provide additional guidance for international research.*

All participants will be recruited from the Virginia Tech, NRV, and Roanoke Valley communities.

Sessions involving laboratory-induced trips and slips for all participants will take place in our research lab on the VT campus ([name]). Also during this session, the investigators will train the participants on the use of the wearable sensors and voice recorders.

Balance training sessions for balance training participants, including all three types of balance training, will be performed in our research lab on the VT campus ([name]) or our research lab leased by VT in the University City Boulevard Mall.

When the two or three weeks of using wearable sensors is complete, the investigators will meet up with the participant to retrieve the sensors from the participant. This meeting will take place either in our research lab on the VT campus or in the University City Boulevard Mall.

Other interactions between the investigator and each participant will occur over the phone to provide any troubleshooting or address any issues with wearable sensor use. At least two telephone calls will be made (one at the end of the first day of sensor use and one at the end of the third day of sensor use), with additional calls up to daily calls possible as needed.

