5.0 Study Design and Statistical Analysis Plan

5.1 *Describe the basic study design/approach (e.g., qualitative study using five focus groups of first year students to describe assimilation into the university community; randomized controlled trial of a behavioral change intervention to increase dietary intake of whole grains; pre- post-test evaluation of new pedagogical techniques to improve adult literacy):*

For our primary objective, a one-group repeated-measures design will be used to validate the use of wearable sensors to capture responses to LOBs. Subjects will use wearable sensors for three weeks to capture responses to naturally-occurring trips and slips during daily life. Subjects will then complete a laboratory session to capture lab-induced LOB responses simultaneously from the wearable sensors and a gold-standard optoelectronic motion capture system.

For our secondary objective, a three-group posttest-only design will be used to compare the effects of three balance training exercises on responses to LOBs after laboratory-induced trips and slips, and two weeks of naturally-occurring real-world trips and slips. Subjects will first complete three weeks of their assigned training. Subjects will then

21-1072 Validation and application of wearable sensors for capturing responses to losses of balance

complete a laboratory session to capture lab-induced LOB responses simultaneously from the wearable sensors and a gold-standard optoelectronic motion capture system. Subjects will then use wearable sensors for two weeks to capture responses to naturally-occurring trips and slips during daily life.

5.2 Describe corresponding data analysis plan/approach (e.g., content analysis of focus group transcripts; descriptive analysis followed by linear regression modeling; nonparametric analysis of pre- and post-test measures):

Hypothesis 1: LOB response measures obtained from the wearable sensors after lab-induced trips and slips will exhibit statistical agreement with the same measures simultaneously obtained from a gold-standard laboratory-based motion capture system.

To address Hypothesis 1, a Bland-Altman analysis will be used to evaluate level of agreement between the two systems. This approach will reveal any measurement bias between the two systems, and provide bounds for these differences.

Hypothesis 2: Real-world LOB responses will show greater variety than laboratory-induced LOB responses.

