8.0 Procedures Involved

8.1 Describe and explain the study design:

For our primary objective, a one-group repeated-measures design will be used to validate the use of wearable sensors to capture responses to LOBs. Non-balance training participants will use wearable sensors for three weeks to capture responses to naturally-occurring trips and slips during daily life. Subjects will then complete a laboratory session to capture lab-induced LOB responses simultaneously from the wearable sensors and a gold-standard optoelectronic motion capture system.

For our secondary objective, a three-group posttest-only design will be used to compare the effects of three balance training exercises on responses to LOBs after laboratory-induced trips and slips, and two weeks of naturally-occurring real-world trips and slips. Balance training participants will first complete three weeks of their assigned training. Subjects will then complete a laboratory session to capture lab-induced LOB responses simultaneously from the wearable sensors and a gold-standard optoelectronic motion capture system. Subjects will then use wearable sensors for two weeks to capture responses to naturally-occurring trips and slips during daily life.

8.2 Provide a description of:

- *All research procedures being performed*
- *If the study has more than one procedure, session, and/or subject population, describe each procedure, session, and/or study*

population separately. For complex studies, you are encouraged to include a figure or chart.

Recruitment and Informed Consent

- Interested participants will respond to our recruitment strategies and contact the investigators.
- The investigators will telephone interested participants and follow the telephone script included in the application to first screen participants for inclusion criteria. If participants satisfy the inclusion criteria, the investigator will continue the telephone conversation and administer the health questionnaire described in an attachment to this application. De-identified information from this health questionnaire will then be reviewed by a health professional with specialist training for the geriatric population. This specialist will be a board certified physician or board certified specialist in geriatric physical therapy.

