21-1072 Validation and application of wearable sensors for capturing responses to losses of balance

weights and using more challenging balance postures. The progression of difficulty will be based on the investigators perception of the improving ability of the participant.

- If the participant is assigned no training, then no such training will be performed.
- All participants will then complete the two types of LOB response measurements described below.

Measure LOB responses in the laboratory:

- Each participant will complete a lab session to assess their response to an LOB after lab-induced trips and slips. This session will take place in our research lab on the VT campus ([name]). During these sessions, participants will wear a safety harness supported overhead to prevent impact with the floor in the event of an unsuccessful balance recovery. First, the appropriate size will be selected from a range of sizes we have in the lab. Second, the investigator will assist the participant in donning the harness, securing all straps and connections, and inspecting and confirming the overall fit. The PI ([name]) has extensive experience with the harnesses, and will train the student investigators in their use.
- Participants will also wear reflective markers so researchers can measure their movements with a laboratory motion capture system. As we have done for years, these markers will be affixed to clothing and skin at selected anatomical landmarks using double-sided tape. [name] will place markers on participants. Markers will be placed bilaterally on the shoes at the toes and heels, ankles, knees, hips, shoulders, elbows, wrists, and on a headband worn around the head.

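### For non-balance training participants, Sections 6.1 and 8.2 imply that the laboratory trip/slip session precedes the three weeks of sensor wear, while Sections 5.1 and 8.1 state the reverse

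*Combined protocol and SAP*

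**What the plan says.** The design sections give one order for the primary-objective cohort. Section 5.1: "Subjects will use wearable sensors for three weeks to capture responses to naturally-occurring trips and slips during daily life". Section 8.1 repeats this and names the cohort: "Non-balance training participants will use wearable sensors for three weeks to capture responses to naturally-occurring trips and slips during daily life". It continues: "Subjects will then complete a laboratory session to capture lab-induced LOB responses simultaneously from the wearable sensors". Both sections give the balance training cohort the reverse order: training, laboratory session, then two weeks of wear.

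Section 6.1 covers both cohorts together: "Sessions involving laboratory-induced trips and slips for all participants will take place in our research lab on the VT campus". Its next sentence is "Also during this session, the investigators will train the participants on the use of the wearable sensors and voice recorders". It makes no exception for non-balance training participants.

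Section 8.2 introduces the measurements with "All participants will then complete the two types of LOB response measurements described below". It describes the laboratory session first and the real-world measurement second. At hand-over, the sensors are given out to "wear over the subsequent three weeks (no balance training participants) or two weeks (TT, NT, and ST participants"). They come back at a further meeting, and no laboratory session is mentioned at that point.

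**The concern.** Hypothesis 2 belongs to the non-balance training cohort (Section 2.2). It asks whether real-world responses are more varied than laboratory responses in the same people. Section 5.2 plans a repeated-measures ANOVA comparing the two environments, with a random subject effect, followed by a Levene-type comparison of residual variability. No order or period term is named.

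The order therefore decides what the real-world data represent. With wear first, they show how these participants respond before any experimental perturbation. With the laboratory first, they show responses after a session of induced trips and slips, using three obstacle heights and three slip hazards (Section 8.2), and after a debriefing (Section 8.6). Section 3.2 reports that perturbation-based training improved responses to laboratory-induced trips and slips, so the protocol itself gives a reason to want the real-world weeks free of such exposure.

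**Working it through.** No figure in the plan bears on this point and no formula applies. The check sets the sequence statements for the non-balance training cohort side by side.

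| Section | What it gives for this cohort | Order |
|---|---|---|
| 5.1 | Three weeks of wear, then the laboratory session | Wear first, stated |
| 8.1 | The same, with the cohort named | Wear first, stated |
| 6.1 | Device training during the laboratory session, for all participants | Laboratory first, implied |
| 8.2 | Laboratory session, hand-over, subsequent three weeks, return meeting | Laboratory first, implied by the sequence of text |
| 14.4 | Apart from balance training, testing is the same for everyone | No separate order given |

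1. **Can 6.1 fit 5.1 and 8.1?** Training on a device has to precede its use at home. Under 5.1 and 8.1 the laboratory session comes after the three weeks, so training given there would come after the wear it is meant to prepare for. Taken literally for this cohort, 6.1 either puts the training too late or forces the laboratory session to the front.

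2. **Does 8.2 settle it?** No. Its sequence reads laboratory first. The separate return meeting points the same way: 6.1 allows it at either the campus laboratory or the University City Boulevard Mall, whereas trip/slip sessions are on campus. If wear came first, the natural place to return the sensors would be the laboratory session, where they are needed anyway.

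3. **Who is affected?** All 30 non-balance training participants, which is the whole Hypothesis 2 cohort. For the 30 balance training participants the order is laboratory then wear in every section, so there is no conflict.

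4. **Which real-world events are affected?** Under the order in 5.1 and 8.1, none follows the laboratory perturbations. Under the order implied by 6.1 and 8.2, all of them do.

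5. **Can the effect be sized?** No. The documents do not give the number of perturbations per laboratory session or any estimate of carry-over from a single session. Nor do they say whether such a session would raise or lower the variability of later real-world responses.

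6. **Which other analyses are touched?** Hypothesis 1 compares two systems recording the same laboratory events simultaneously, so the order drops out. Hypotheses 3 to 5 concern the balance training cohort.

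**The case against.** The strongest reply is that the order is explicit where the design is defined. Sections 5.1 and 8.1 agree, and each gives the two cohorts opposite orders, which looks deliberate. Section 6.1 answers where procedures happen and states no sequence. Section 8.2 may be arranged by type of measurement, and its word for the following weeks can be read as following the briefing in the same sentence. Section 14.4 answers a question about subject numbers and cannot establish an order. All of this stands, and it means the laboratory-first order is implied and nowhere stated. It does not remove the conflict in 6.1, which ties device training to the laboratory session for everyone, and 8.2 does not name the visit at which this cohort receives the sensors.

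Three stronger readings are tempting, and the documents do not support them.

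- A reader might infer that these participants would wear the sensors without instruction. Section 8.2 provides a briefing at hand-over and telephone calls after the first and third days. Section 7.3 promises detailed instructions, Section 8.4 covers training on charging, and Section 20.2 adds an illustrated packet for home use.
- A reader might infer that the order would differ from one participant to the next. Nothing in the documents suggests this.
- A reader might infer that laboratory-first order would certainly bias Hypothesis 2. The training described in Section 7.1 is six sessions (two a week for three weeks), with up to 40 perturbations per session in the treadmill arm. The documents do not show that one assessment session acts in the same way.

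It is also fair to say that any fixed order ties environment to sequence, and reconciling the text does not change that. What it secures is narrower: real-world data collected before any laboratory perturbation, as the design section intends.

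**Conclusion.** The protocol gives conflicting operational sequences for the cohort on which Hypothesis 2 rests. Sections 5.1 and 8.1 state wear first; 6.1 and 8.2 imply laboratory first; both cannot apply. If 6.1 and 8.2 were followed, all real-world events in these 30 participants would come after laboratory perturbations and debriefing. Carry-over is then possible, with unknown size and direction.

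This rests on two assumptions: that device training is meant to precede home use, and that staff may work from the setting and procedures sections as well as from the design section. If they work only from 5.1 and 8.1, the real-world data stay free of prior laboratory exposure and the fault is one of wording. The correction is worth making because it covers every real-world event in Hypothesis 2 and costs almost nothing.

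**What to change.** Reconcile 6.1 and 8.2 with 5.1 and 8.1:

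- State in 6.1 and 8.2 that non-balance training participants are trained on the sensors and recorder at a hand-over visit before the three weeks of wear, and complete the laboratory session afterwards. The existing first laboratory visit, once eligibility is confirmed, could serve. The signing of consent should not be used to define this visit, because Section 24.1 places written consent before the DEXA scan for participants who need a new scan.
- Limit the 6.1 sentence on device training during the laboratory session to balance training participants.
- Say that non-balance training participants can return the sensors at the laboratory session.
- Record the dates of hand-over, wear and laboratory session for each participant, so that the actual order is known at analysis.

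The cost is a wording amendment and a few recorded dates. If hand-over uses the first laboratory visit and return uses the laboratory session, no visit is added.
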